5.4 Informational Endpoints

5.4.1 Patient Reported Outcomes

Patient-reported outcomes are informational endpoints to assess Health-Related Quality of Life at baseline, 1, 6, 12 months and will be assessed at 3 and 5 years throughout the remaining duration of the trial. These PRO endpoints will be evaluated in the ~2600 subjects of ABSORB IV. The following questionnaires will be used in this study:

- Seattle Angina Questionnaire-7 (SAQ-7) to assess disease-specific Quality of Life
- EuroQoL 5D (EQ-5D) survey to assess overall health status

The PROs will be analyzed to evaluate the relationship between quality of life and cardiovascular events that occurs post-PCI and to substantiate the clinical impact of the angina events identified in the trial.

5.4.2 Health Economics

During the course of the trial, the Sponsor (or the health economic core laboratory) will collect health economic data. The data may include billing information and claims data for the index hospitalization and for subsequent hospitalizations during the follow-up period, for sites located in the United States only. Patients will be asked to provide consent to access billing information for the purposes of conducting economic analysis of the trial.

Additional information regarding medical resource utilization may also be collected throughout the trial, including but not limited to: laboratory services, diagnostic procedures, or pharmacy records.

6. SUBJECT SELECTION AND WITHDRAWAL

6.1 Subject Population

Subjects registered into this Clinical Investigation will be male and female subjects derived from the general interventional cardiology population. The Clinical Investigation will register approximately 2600 subjects, with up to three *de novo* native coronary artery lesions in a maximum of two epicardial vessels and a maximum of two lesions per epicardial vessel, who meet all eligibility criteria, have provided written Informed Consent and have been registered in the trial.

6.2 Subject Screening and Informed Consent

6.2.1 Subject Screening and Informed Consent

Please refer to **section 6.2.1** and **6.2.2** of ABSORB III Protocol ([REDACTED], August 16, 2018) for the relevant information about subject screening and informed consent.

6.3 Eligibility Criteria

Assessment for general eligibility criteria is based on the medical records of the site and interview with a candidate subject. Clinical and laboratory test of the eligibility assessment shall be per site standard of care. If some of the protocol required tests are not included in the site's standard tests, they must be done, but after written Informed Consent has been obtained. Subjects must meet ALL of the inclusion criteria to be considered for the clinical evaluation. If ANY of the exclusion criteria are met, the subject is excluded from the clinical evaluation and cannot be registered. Please see **Protocol Summary**, Inclusion Criteria and Exclusion Criteria, for details of the eligibility criteria of ABSORB IV.

6.4 Point of Registration

During the randomization phase, the subject is considered randomized after IVRS has been called and a device has been assigned (Absorb BVS or XIENCE). The subject is considered registered and in the ITT population at the point of randomization. Once randomization is completed and a treatment arm is assigned, crossover is not permitted. [REDACTED]

Refer to **Appendix IV** and **Figures 1 and 2** for further registration details.

6.5 Subject Discontinuation

Please refer to **section 6.5** of ABSORB III Protocol ([REDACTED], August 16, 2018) for the relevant information about subject discontinuation.

7. TREATMENT AND EVALUATION OF SAFETY AND EFFECTIVENESS

7.1 *Baseline*

7.1.1 *Baseline Laboratory Assessments to Confirm Subject Eligibility*

Subject preparation will be in accordance with standard hospital policy for the care of interventional cardiology subjects.

7.1.2 *Subject History*

Subject history will include demographics (e.g., age, gender)⁵⁶, cardiac history including but not limited to Canadian Cardiovascular Society (CCS) and Braunwald classification of angina, history of myocardial infarction, diabetes mellitus, hypertension, hypercholesterolemia, previous CABG and PCI, and concomitant cardiovascular medications (Refer to **Appendix II** for Definitions). In addition, measurements of weight, height, and resting blood pressure will be collected.

7.1.3 *Patient-Reported Outcomes Assessment*

All ~2600 subjects in ABSORB IV will complete the following Patient Reported Outcome questionnaires prior to the index procedure*.

- EuroQoL 5D (EQ-5D) survey to assess overall health status.
- Seattle Angina Questionnaire-7 (SAQ-7) to assess disease-specific Quality of Life.

Please refer to **section 7.1.3** of ABSORB III protocol ([REDACTED], August 16, 2018) for the details regarding each questionnaire.

*Every effort should be made to have subjects complete all three patient reported outcomes questionnaires prior to the procedure. However, in situations where this is absolutely not possible, subjects may complete them post-procedure, prior to discharge. Subjects who complete their questionnaires post-procedure should base their responses on their condition prior to the procedure.

7.2 *Pre-Procedure*

7.2.1 *Pre-Procedure Laboratory Assessment*

The following laboratory assessments need to be obtained prior to the index procedure or at the time of the index procedure depending on the assessment and condition of the subject.

Table 7.1 Baseline Laboratory Assessment

⁵⁶ Demographics include age, gender, post-menopausal status, date of birth, race/ethnicity, highest level of education, employment status and household income.

Within 21 days prior to procedure†

Platelet and White Blood Count
Hemoglobin
Serum Creatinine
HbA1c‡
Estimated GFR*

Within 7 days prior to procedure

Pregnancy test (if applicable)

Within 48 hours prior to procedure

12-lead ECG (within 24 hours preferred)
Creatine kinase (CK)
Creatine kinase myocardial-band isoenzyme (CK-MB)
Troponin (if suspected acute coronary syndrome, within 24 hours)

†The 21-day lab results must be known prior to index procedure.

‡ HbA1c is to be collected in diabetic subjects only, and its result is not needed prior to the index procedure.

* Glomerular Filtration Rate

The following applies to cardiac enzyme measurement pre-procedure and during the procedure.

- All patients admitted with the diagnosis of possible acute coronary syndrome (including unstable angina, NSTEMI or STEMI) must have at least one and preferably 2 or more complete sets of cardiac biomarkers (a set consisting of troponin (I or T), CK and CK-MB) measured within 24 hours of procedure. Measurements should be at least 6 hours apart if multiple measurements were taken.
- If the patient has stable coronary artery disease or silent ischemia, a pre-procedure CK and CK-MB must be drawn, but may be obtained during the procedure from the arterial sheath but prior to any angioplasty. The angioplasty procedure may then be performed before the results are known.
- To assist in the determination of peri-procedural MI, during the procedure, all patients with an acute coronary syndrome (including unstable angina, NSTEMI or STEMI) must have troponin, CK and CK-MB drawn from the arterial sheath prior to first balloon inflation.

For subjects having staged procedures, the protocol-required pre-procedure and post-procedure cardiac enzyme and 12-lead ECG assessments must be repeated for the staged procedure in the same manner as done for the original index procedure.

7.2.2 Dual Anti-Platelet Medications

Subjects selected for treatment with Absorb BVS or XIENCE must receive a loading dose of ≥ 300 mg of aspirin within 24 hours, regardless of whether the patient was previously taking aspirin. For patients undergoing staged procedure who have not been discharged and have been prescribed daily aspirin while in hospital, no aspirin reloading is required.

For patients with stable coronary symptoms, silent ischemia, or acute coronary syndromes in whom all measured troponin and CK-MB values were within normal limits, pre-loading with clopidogrel between 3 and 24 hours prior to the index procedure or prasugrel or ticagrelor between 1-24 hours prior to the index procedure is strongly recommended. If the above loading time periods are not possible, the P2Y12 inhibitor must be administered in all patients no later than 1 hour after the procedure. If the subject receives less than the required amount of the loading dose for a P2Y12 receptor inhibitor, the investigator is to give the remaining amount of the same agent in the next 24 hours and within the protocol required timeframe.

Note: The biomarker measurements in patients with stable coronary symptoms and silent ischemia may be pending at the time of the procedure, or may be drawn from the arterial sheath prior to first balloon inflation; such patients may still be randomized, and a P2Y12 receptor inhibitor must be administered no later than 1 hour after the procedure.

For patients with acute coronary syndromes in whom any troponin or CK-MB value at any time prior to the index hospitalization was elevated, one of two treatment options must be used a) a loading dose of clopidogrel between 3 and 24 hours prior to the procedure or prasugrel or ticagrelor between 1-24 hours prior to the index procedure must be given, OR b) an intravenous GP IIb/IIIa inhibitor or cangrelor (see below) must be administered prior to and/or during PCI but prior to first balloon inflation, per institution standard of care. If an intravenous GP IIb/IIIa inhibitor is given, a P2Y12 receptor inhibitor must be given within 1 hour following the index procedure. If intravenous cangrelor is used, the timing of the first administration of the P2Y12 receptor inhibitor should be as follows: clopidogrel or prasugrel are administered at the time of discontinuation of the cangrelor infusion; ticagrelor may be administered before, during, or immediately upon discontinuation of the cangrelor infusion. Ticagrelor is the preferred P2Y12 receptor inhibitor in cangrelor-treated patients. Cangrelor should be maintained 2-4 hours post procedure according to label.

Note: If the subject receives less than the required amount of the loading dose for a P2Y12 receptor inhibitor, the investigator is to give the remaining amount of the same agent in the next 24 hours and within the protocol required timeframe.

The protocol required loading dose may be omitted in a) stable CAD or ACS patients maintained on chronic P2Y12 receptor inhibitor for ≥ 7 days, and b) patients who received a P2Y12 receptor inhibitor loading dose 1-7 days prior to the procedure and who have been maintained on a daily dose since. However, it is strongly recommended that stable patients on chronic clopidogrel are reloaded with a P2Y12 receptor inhibitor. For ACS patients on chronic clopidogrel, they must be reloaded with a P2Y12 receptor inhibitor if they did not already receive a loading dose of clopidogrel, prasugrel, or ticagrelor in the 24 hours prior to the procedure.

Ticlopidine may be used as a substitute at a dose in accordance with standard hospital practice only if the subject develops hypersensitivity or intolerance to clopidogrel, prasugrel, or ticagrelor during the trial.

Refer to respective prescribing information for P2Y12 receptor inhibitor for further details regarding loading practice.

Cangrelor may be used pre-PCI at operator discretion as per local practice in any patient (but should be used similarly in patients randomized to ABSORB and XIENCE): a pre-PCI loading dose of 30 $\mu\text{g}/\text{kg}$ IV followed by an IV infusion of 4 $\mu\text{g}/\text{kg}$ for at least 2 hours and for a maximum of 4 hours may be used, in conjunction with an oral P2Y12 inhibitor. If ticagrelor is selected, the ticagrelor loading dose may be given before, during or immediately upon discontinuation of the cangrelor infusion. If clopidogrel or prasugrel are selected, a clopidogrel or prasugrel loading dose should be given immediately upon discontinuation of the cangrelor infusion, even if a loading dose was given earlier.

For subjects having staged procedures, the pre-procedure administration regimen of aspirin and P2Y12 receptor inhibitor (dosage requirements and timing) must be repeated prior to the staged

procedure in the same manner as done for the original index procedure. If the subject has not been discharged between the index and staged procedures, and has received daily aspirin while in hospital, no aspirin reloading is required (see above).

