Antiplatelet⁴⁸ Therapy	Antiplatelet Medication Loading Dose: 
● Aspirin: Subjects must receive a loading dose of ≥ 300 mg of aspirin within 24 hours before the procedure, regardless of whether the patient was previously taking aspirin. For patients undergoing staged procedure who have not been discharged and have been prescribed daily aspirin while in hospital, no aspirin reloading is required.● P2Y12 receptor inhibitors: either clopidogrel, prasugrel or ticagrelor may be used as per standard of care and per label indications.
○ Clopidogrel: a peri-procedural loading dose 600 mg is required○ Prasugrel: a peri-procedural loading dose of 60 mg is required○ Ticagrelor: a peri-procedural loading dose of 180 mg is required.● For patients with stable coronary symptoms, silent ischemia, or acute coronary syndromes in whom all measured troponin and CK-MB values were within normal limits, pre-loading with clopidogrel between 3 and 24 hours prior to the procedure or prasugrel or ticagrelor between 1-24 hours prior to the index procedure is strongly recommended. If the above loading time periods are not possible, a P2Y12 inhibitor must be administered in all patients no later than 1 hour after the procedure. If the subject receives less than the required amount of the loading dose for a P2Y12 receptor inhibitor, the investigator is to give the remaining amount of the same agent in the next 24 hours and within the protocol required timeframe. 
Note: The biomarker measurements in patients with stable coronary symptoms and silent ischemia may be pending at the time of the procedure, or may be drawn from the arterial sheath prior to first balloon inflation; such patients may still be randomized, and a P2Y12 receptor inhibitor must be administered no later than 1 hour after the procedure.
 
For patients with acute coronary syndromes in whom any troponin or CK-MB value at any time prior to the index hospitalization was elevated, one of two options must be given a) a loading dose of

--	---

⁴⁸ ABSORB IV will allow the use of FDA approved P2Y12 inhibitors. Loading and maintenance dosages of all P2Y12 inhibitors should follow respective prescribing information. If outside the US, country specific approvals are allowed.

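### For stable, silent-ischemia or biomarker-negative ACS patients not pre-loaded and given cangrelor with clopidogrel or prasugrel, ABSORB IV sets two oral-dose timings without saying which governs

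*Protocol*

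**What the plan says.** All the text is in ABSORB IV section 7.2.2 (Dual Anti-Platelet Medications), with a near-identical copy in the ABSORB IV Protocol Summary under Antiplatelet Therapy. Three paragraphs matter.

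- **Stable, silent-ischemia and biomarker-negative ACS paragraph.** It covers stable symptoms, silent ischemia and "acute coronary syndromes in whom all measured troponin and CK-MB values were within normal limits". Pre-loading is strongly recommended. "If the above loading time periods are not possible", the rule is that "the P2Y12 inhibitor must be administered in all patients no later than 1 hour after the procedure". A note repeats the limit for stable and silent-ischemia patients whose biomarkers are pending: "such patients may still be randomized, and a P2Y12 receptor inhibitor must be administered no later than 1 hour after the procedure". The Summary has the same deadline: "a P2Y12 inhibitor must be administered in all patients no later than 1 hour after the procedure". None of these sentences mentions cangrelor.
- **Biomarker-positive ACS paragraph.** Here the 1-hour limit is attached to use of a GP IIb/IIIa inhibitor. Cangrelor has its own timing for the first oral dose: "clopidogrel or prasugrel are administered at the time of discontinuation of the cangrelor infusion", with ticagrelor allowed before, during or at the end of the infusion. The infusion is described this way: "Cangrelor should be maintained 2-4 hours post procedure according to label".
- **General cangrelor paragraph.** The operator may use cangrelor in any patient, as a pre-PCI bolus followed by an infusion lasting 2 to 4 hours in total. If clopidogrel or prasugrel is chosen, "a clopidogrel or prasugrel loading dose should be given immediately upon discontinuation of the cangrelor infusion, even if a loading dose was given earlier".

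A separate paragraph lets some patients omit the required load, such as those on a chronic P2Y12 inhibitor for at least 7 days. ACS patients on chronic clopidogrel must still be reloaded unless they were loaded in the previous 24 hours.

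**The concern.** The general cangrelor paragraph reaches every clinical group, including the one under the 1-hour deadline. For a patient in that group who was not pre-loaded and receives cangrelor with clopidogrel or prasugrel, one sentence fixes the oral dose by the clock after the procedure. The other fixes it by the end of the infusion. The section does not rank them.

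Sites can therefore treat the same patient in three ways: an early dose, a dose at the end of the infusion, or both. The deadline is worded as *must* and the cangrelor timing as *should*, so a site that follows only the cangrelor text can breach mandatory wording. The section also requires the regimen to be repeated for staged procedures, so the question can recur in one patient.

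**Working it through.** No sample size, power or alpha figure is involved. The check compares scope and then does clock arithmetic.

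**Step 1: who is under both rules.** All of these must hold:
1. stable symptoms, silent ischemia or biomarker-negative ACS (the deadline's paragraph);
2. not pre-loaded within the recommended window (the deadline's condition);
3. not entitled to omit the load;
4. given cangrelor (allowed in any patient);
5. given clopidogrel or prasugrel. Ticagrelor may be given before or during the infusion, so it can meet both rules.

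**Step 2: when the end-of-infusion dose falls.** The general paragraph gives an infusion length L of 2 to 4 hours in total. Let T be the procedure length in hours, which the documents do not give, and assume the infusion starts with the procedure. Then

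end of infusion, counted from end of procedure = L − T,

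and the 1-hour limit is met when L − T ≤ 1, that is, T ≥ L − 1. For L = 2 this needs T ≥ 1; for L = 4 it needs T ≥ 3.

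| T assumed (h) | L = 2: 2 − T (h) | L = 4: 4 − T (h) | 1-hour limit |
|---|---|---|---|
| 0.5 | 1.5 | 3.5 | always missed |
| 1 | 1 | 3 | met only at the 2-hour minimum |
| 1.5 | 0.5 | 2.5 | depends on L |
| 2 | 0 | 2 | depends on L |
| 3 | −1 | 1 | always met |

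So the end-of-infusion dose always misses the limit for T under 1 h, may miss it for T from 1 h to under 3 h, and meets it for T of 3 h or more. If the infusion starts before or after the procedure does, replace T by the time from infusion start to procedure end.

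**Step 3: can both rules be met?** Yes, in two ways. The infusion may end by 1 hour after the procedure (Step 2). Or a load is given by 1 hour and a second on stopping the infusion, which the general paragraph allows for by asking for the later load whether or not one was given before.

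**Step 4: a second mismatch.** The biomarker-positive paragraph counts 2 to 4 hours from the end of the procedure; the general paragraph counts 2 to 4 hours in total. For any T above zero, and with the same starting assumption, these are different infusions: the first has total length T + 2 to T + 4 hours.

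**The case against.** The strongest reply is that the drug-specific text is meant to govern. The deadline's paragraph never mentions cangrelor. The biomarker-positive paragraph refers the reader onward to the cangrelor text and gives cangrelor its own timing. Cangrelor is optional, pre-loading is strongly recommended, and ticagrelor is named as the preferred agent with cangrelor, so the affected group should be small. That reading is natural, and the narrowing stands. The exception is nevertheless not written. The biomarker-positive paragraph shows how it could have been, by tying its 1-hour limit to GP IIb/IIIa use; the deadline's paragraph has nothing similar and says all patients.

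One might also say that cangrelor itself satisfies the deadline. But the section names clopidogrel, prasugrel and ticagrelor as the agents to load and describes cangrelor as given together with an oral agent.

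Some stronger readings are tempting and are not supported:

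- *Every cangrelor patient is affected, and the gap is 1 to 3 hours with no overlap.* That figure (2 − 1 = 1 to 4 − 1 = 3) uses the wording that counts from the end of the procedure. That wording belongs to biomarker-positive ACS, where no 1-hour limit is tied to cangrelor. For the group at issue, the gap depends on T.
- *A protocol deviation is unavoidable.* Two loading doses, or a long enough procedure, satisfy both rules literally. The wording that speaks of a first oral dose at discontinuation is in the biomarker-positive paragraph.
- *Antiplatelet cover is lost, or 30-day TLF is affected.* With a late oral dose the patient is on cangrelor until that dose, and no figure in the documents links this timing to the endpoint. The section asks that cangrelor be used alike in both arms, so no between-arm bias is identified.

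**Conclusion.** A real but minor conflict between two stated rules, confined to the group in Step 1 of the working. Within it, following only the cangrelor timing certainly breaches the deadline when the procedure is shorter than 1 hour, possibly from 1 to under 3 hours, and not from 3 hours. These cut-points rest on the assumption that the infusion starts with the procedure. The documents give neither procedure length nor the number of patients in this group. Where the infusion ends too late, the site either misses a mandatory deadline or gives two loading doses hours apart, and the protocol does not say that it intends the second dose as the way to meet the deadline. The two descriptions of infusion duration also need to agree. No effect on the trial's result is shown.

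**What to change.** Reconcile ABSORB IV section 7.2.2 and the Antiplatelet Therapy part of the ABSORB IV Protocol Summary together, so that:

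- each clinical group has one timing rule for the oral agent when cangrelor is used;
- infusion duration is defined once, either as total time or as time after the procedure;
- the text says how an earlier load is handled, including whether a second load is intended.

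Which timing is right is a clinical decision and is not addressed here. The cost is protocol wording and a site letter. If index procedures are already complete, a short documented rule for classifying deviations in these patients would still be useful.

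### ABSORB IV ties its mandatory pre-PCI antiplatelet cover to markers raised before the index hospitalization, so read literally it omits ACS patients who first test positive in hospital

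*Protocol*

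**What the plan says.** The text is in ABSORB IV Section 7.2.2 (Dual Anti-Platelet Medications) and in the Antiplatelet Therapy entry of the ABSORB IV Protocol Summary. It sorts patients into two groups by cardiac markers.

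- **Mandatory group.** Section 7.2.2 applies this rule when, in an ACS patient, "any troponin or CK-MB value at any time prior to the index hospitalization was elevated"; the Protocol Summary uses the same trigger. These patients must have either clopidogrel 3 to 24 hours before the procedure (or prasugrel or ticagrelor 1 to 24 hours before), or an intravenous GP IIb/IIIa inhibitor or cangrelor started before the first balloon inflation.
- **Recommended group.** This takes stable patients, silent ischemia, and "acute coronary syndromes in whom all measured troponin and CK-MB values were within normal limits". The same oral pre-loading windows are strongly recommended here but not required. The fallback, timed from the procedure, reads "If the above loading time periods are not possible, the P2Y12 inhibitor must be administered in all patients no later than 1 hour after".

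Three other provisions bear on the point. NSTEMI within two weeks of the index procedure is eligible (ABSORB IV Protocol Summary, General Inclusion Criteria). Patients admitted with possible ACS must have at least one full marker set in the 24 hours before the procedure (Protocol Summary, Cardiac Biomarker Collection; Section 7.2.1). ACS patients must also have a sample drawn from the arterial sheath during the procedure (Section 7.2.1).

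**The concern.** The two groups should be complements among ACS patients: any raised value in one, no raised value in the other. They are not, because the mandatory group looks only at values from before the index hospitalization while the recommended group looks at all measured values. The patients left out are ordinary ones for this trial: admitted with suspected ACS and found positive on a draw made after admission.

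What is at stake is patient safety and consistent conduct, not the statistical design. For these patients the text imposes no requirement that cover be in place before the first inflation. A site following the words and a site following the evident intent would also disagree on whether omitting that cover is a protocol deviation.

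**Working it through.** No arithmetic applies to the gap itself; the check is to apply the two rules to each kind of ACS patient.

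| ACS patient | Mandatory rule | Recommended rule |
|---|---|---|
| A value raised before the index hospitalization | Applies | Does not apply: not all values normal |
| All measured values normal | Does not apply | Applies |
| No raised value before admission, a raised value after it | Does not apply: nothing raised before the hospitalization | Does not apply: not all values normal |

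**Can the third patient occur?** Yes. Recent NSTEMI is eligible, and the required marker set is for admitted patients within 24 hours of the procedure, so a draw after admission is a normal event. The Protocol Summary repeats the trigger wording, so neither place corrects the other.

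**What was meant?** Four features point to any raised value before the procedure.

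1. The companion rule speaks of all measured values, whose natural complement is any raised measured value.
2. A note in Section 7.2.2 allows marker results to be pending at the procedure for stable and silent-ischemia patients and does not mention ACS patients. That suggests ACS results were meant to guide treatment.
3. Section 7.2.3 refers to biomarker-positive ACS with no hospitalization limit.
4. The periprocedural MI definition in ABSORB IV Appendix II classifies ACS patients by marker levels up to the procedure.

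**Does another provision impose the missing requirement?** Each was checked for whether it requires cover before the first inflation in the third patient.

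- Aspirin loading: required, but it is not the P2Y12 or intravenous cover at issue.
- Peri-procedural P2Y12 load: required, but the fallback limit is one hour after the procedure.
- Chronic clopidogrel users: "For ACS patients on chronic clopidogrel, they must be reloaded with a P2Y12 receptor inhibitor" unless loaded in the previous 24 hours. This covers only patients already on clopidogrel.
- Cangrelor: allowed in any patient, at operator discretion (Section 7.2.2).
- GP IIb/IIIa inhibitor with unfractionated heparin: recommended for biomarker-positive ACS, not mandatory (Section 7.2.3).
- GP IIb/IIIa inhibitor with bivalirudin: the advice against routine use is lifted for an ACS patient who was not pre-loaded and in whom cangrelor is not used. This permits use and does not require it (Section 7.2.3).

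None of these supplies the requirement. The most exposed case is an in-hospital-positive patient with no P2Y12 inhibitor on board, treated on bivalirudin, whose operator uses neither intravenous option.

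**The case against.** The strongest reply is that this is a slip of one word, that an experienced operator will read it as intended, and that Section 7.2.3 and the discretionary cangrelor provision already deal with most of these patients. Much of that stands. The intent is clear, the residual group is narrow, and the documents do not allow it to be counted. But the provisions relied on recommend or permit, whereas the rule at issue is mandatory. A mandatory treatment rule used at approximately 140 sites should not depend on readers correcting it.

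A reader might infer more than the documents support.

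- **That these patients go without antiplatelet treatment.** They do not: aspirin and a P2Y12 load remain required.
- **That their oral P2Y12 dose may come later than the mandatory rule would allow.** With the GP IIb/IIIa option that rule itself says "If an intravenous GP IIb/IIIa inhibitor is given, a P2Y12 receptor inhibitor must be given within 1 hour following the index procedure". The latest time is one hour after the procedure under either rule, a difference of 1 − 1 = 0 hours. With cangrelor no figure can be given, because Section 7.2.2 uses two clocks. One sentence says "Cangrelor should be maintained 2-4 hours post procedure according to label"; another describes a pre-PCI bolus followed by an infusion of 2 to 4 hours.
- **That the comparison of Absorb with XIENCE is biased.** The trigger does not depend on the assigned device, and nothing in the documents suggests that the gap falls unequally.

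**Conclusion.** The rule is wrong as written, and the point is minor. Read literally, an eligible ACS patient whose first raised troponin or CK-MB is measured during the index hospitalization falls in neither group and loses one yes-or-no requirement: cover in place before the first balloon inflation.

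The conclusion rests on a literal reading and on counting a draw made after admission as within the hospitalization. The share of ACS patients affected is not in the documents and is not estimated.

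**What to change.** Make the two groups complements in both places.

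- **Mandatory rule** (Section 7.2.2 and Protocol Summary): replace the limit at the index hospitalization with *prior to the index procedure (including during the index hospitalization), excluding the arterial-sheath sample*.
- **Recommended rule** (same two places): refer to *all troponin and CK-MB values measured prior to the index procedure, excluding the arterial-sheath sample*.

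The sheath sample is excluded because it is drawn during the procedure, to help determine peri-procedural MI, and cannot guide pre-loading. The existing rules on when a loading dose may be omitted stay as they are.

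The wording should not be extended to values before a staged procedure, even though Section 7.2.2 says that "the pre-procedure administration regimen of aspirin and P2Y12 receptor inhibitor (dosage requirements and timing) must be repeated prior to the staged" procedure. Section 7.4.2 requires CK-MB in all subjects at 6 to 12 hours and again at 18 to 24 hours (or at discharge from 16 hours) after the index procedure. An ordinary post-PCI rise on those draws would then move a marker-negative ACS patient into the mandatory group for the staged procedure.

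The cost is a short protocol amendment that extends a required drug step to more patients. It needs IRB/EC submission and written approval before use (ABSORB III Section 14.1, applied to ABSORB IV by its Section 11). No new tests or data are needed. The documents do not state whether patients are still being treated; if none are, the change has no prospective effect and serves only to clarify how deviations are judged.
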